1. Intratumoral injection with calcium, followed by electrical pulses.
2. Intratumoral injection with bleomycin, followed by electrical pulses.

Randomization will be done separately on each metastasis

Objectives

Primary Objective

The primary objective is to evaluate and compare response rate of calcium electroporation and electrochemotherapy on cutaneous metastases. Response will be evaluated individual on each treated metastasis by clinical examination and documented by clinical photo before and after treatment. Evaluation is performed according to RECIST-like guidelines.

Secondary Objective

The secondary objective is to register adverse events for calcium electroporation and electrochemotherapy respectively. Adverse Events (AE) and Serious Adverse Events (SAE) will be evaluated and graded according to Common Terminology Criteria for Adverse Events (CTCAE) version 4.0.

Tertiary Objective

The tertiary objective is to register if calcium affects the current strength in electroporation treatments. Maximum given current in metastases treated with calcium will be compared to maximum given current in metastases treated with bleomycin.

Trial Design

Trial Design for Treatment of Cutaneous Metastases

It is a randomized double blinded phase II study (adapted from Denmark) comparing the effect of calcium electroporation with ECT with bleomycin on patients with cutaneous metastases of any histology. As calcium and bleomycin are administered intratumoral, only small metastases from 0.5-3cm will be treated. The treatments will be compared in tumor response and adverse events. Treatment will be done in a palliative purpose.

Cancer patients with cutaneous involvement have often several metastases. A maximum of ten metastases will be included per patient. One to six metastases (depending on the patient's number of metastases) will be numbered 1-6 and randomized into one of two treatment arms:

1. Intratumoral calcium followed by electroporation
2. Intratumoral bleomycin followed by electroporation

Randomization will be performed separately on each metastasis, so the patient may receive both treatments. Calcium and bleomycin will be mixed into syringes labeled with numbers according to the metastases and both treating doctor and patient will be blinded to the content of the syringes.

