If the patient has more than six metastases, then one to four metastases will be used for biopsy. The treatment of these metastases will be known, and biopsies will be performed before and after treatment. The metastases used for biopsy will not be evaluated on response.

- One to six metastases: All metastases will be evaluated on response, no biopsies.
- Seven metastases: six metastases will be evaluated on response and one metastasis will be used for biopsy before and/or after treatment with calcium.
- Eight Metastases: six metastases will be evaluated on response and two metastases will be used for biopsy before and/or after treatment with calcium and bleomycin respectively.
- Nine Metastases: six metastases will be evaluated on response and three metastases will be used for biopsy before and/or after treatment with calcium and bleomycin respectively.
- Ten Metastases: six metastases will be evaluated on response and four metastases will be used for biopsy before and/or after treatment with calcium and bleomycin respectively.

The treatment will be performed in local or general anesthesia depending on location and number of metastases. Bleomycin/calcium will be administered intratumorally and immediately after the electrode will be placed on the metastasis. The electric pulses are generated using a cliniporator according to ESOPE (European Standard Operating Procedure of Electrochemotherapy). It is a once only treatment and the patients will be followed up with regular clinical controls for six months. At follow up six months after treatment, the randomization code for the one patient will be revealed. If the patient agrees, biopsies will then be taken from an area treated with calcium and an area treated with bleomycin. Last visit will be one year after treatment.

To identify the metastases at follow up visits, the metastases will be marked with a pen, numbered and documented with clinical photos at baseline.

Randomization

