The metastases are randomized by block randomization and are done separately in each patient. The randomization is performed by an extern unit, using the computer program nQuery Adviser 7.0. The bleomycin and calcium are mixed and labeled by an extern unit, and since both calcium and bleomycin are transparent and identical in volume, it is possible to label the syringes in a manner to blind the treating doctor. The syringes are labeled with numbers according to the metastases so syringe number '1' goes to metastasis number '1' and so on. The randomization code is kept behind locked doors, and is not accessible to the treating doctor. The randomization code is revealed for each patient after follow up, 6 months after treatment.

The randomization code can be revealed before completion of the investigation, if the investigator believes that the treatment causes so serious unexpected events or reactions, that a continuation of treatment is unacceptable.

As the randomization is done separately in each patient, it is possible to break the code for the individual patient, without breaking the code of the other participants.

Dose

The dose of calcium chloride was amended to 220 mmol/L from 168 mmol/L in this trial.

Volume of calcium chloride is dependent on tumor volume. Smaller tumors should have bigger volume per cm^3 , as smaller tumors are expected to have a bigger loss of injected medicine into the surrounding tissue. The dose volume is calculated according to the 'European Standard Operating Procedure of the Electrochemotherapi (ESOPE)':

Calcium

Calcium chloride 220 mmol/L (9 mg/ml):

- Tumor $< 0,5 \text{ cm}^3$ – 1 ml / cm^3 tumor volume
- Tumor $> 0,5 \text{ cm}^3$ – 0,5 ml/ cm^3 tumor volume

Tumor volume = $ab^2\pi/6$ (a=longest diameter, b= longest diameter perpendicular to a)

Bleomycin

Both dose and volume of bleomycin is standard according to ESOPE

Bleomycin 1000 IU/ml:

- Tumor $< 0,5 \text{ cm}^3$ – 1 ml / cm^3 tumor volume
- Tumor $> 0,5 \text{ cm}^3$ – 0,5 ml/ cm^3 tumor volume

Tumor volume = $ab^2\pi/6$ (a=longest diameter, b= longest diameter perpendicular to a)

Maximum of injected bleomycin per tumor will be 1500 IU and total dose per treatment 7500 IU. Normal maximum limit for bleomycin is 15.000 IU/ m^2 body surface area.

Bleomycin and calcium chloride are mixed and labeled according to current guidelines. The mixtures will be used in a maximum of 6 hours after mixing.

The Electrical Pulses

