This is a randomized non-inferiority study comparing calcium electroporation with electrochemotherapy with intratumoral injection of bleomycin. For dimensioning tumor number, analysis of non-inferiority study is used. Tumor response is evaluated at each follow up with surveying. Documentation is done with digital color photography, including a ruler to estimate tumor size. Primary evaluation of the response will be based on criteria similar RECIST guidelines 1.1. Tumor response was analyzed using Fisher's exact test on objective response 6 months after treatment.

Response rate of tumors ≤ 3 cm treated with ECT with bleomycin is 85-100% (existing data). In this study, we have chosen not to put the expected response rate for ECT too high, but estimate it to 85%. We have no clinical results for the treatment of calcium electroporation, but on the basis of preclinical studies, the response rate for calcium electroporation is estimated to 70%. In order to detect a clinical difference in the two treatments of 15%, with a significant level of 0.1, and a power

of 80%, a minimum of 34 evaluable tumors need to be included. (Sample Size Calculator: https://www2.ccrb.cuhk.edu.hk/stat/proportion/tspp_sup.htm)

The metastases are evaluable 4 weeks after treatment. If a patient is excluded from the protocol before 4 weeks follow up, the patient will be replaced.

The number of patients that are being pulled out of the trial will be listed and primary reason for the exclusion will be described.

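### Replacing any patient excluded before week 4 lets treated, randomised metastases drop out of the response rates, and the planned listing does not show those losses by metastasis or arm

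*Combined protocol and SAP*

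**What the plan says.** The randomised unit is the metastasis. Trial Design for Treatment of Cutaneous Metastases states "One to six metastases (depending on the patient's number of metastases) will be numbered 1-6 and randomized into one of two treatment arms", and adds: "Randomization will be performed separately on each metastasis, so the patient may receive both treatments". The Randomization section states "The metastases are randomized by block randomization and are done separately in each patient"; it gives no allocation ratio. All treatment is given in one session: "It is a once only treatment and the patients will be followed up with regular clinical controls for six months".

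The Statistical analysis section expresses the sample size as at least 34 evaluable tumours and defines when a tumour reaches that status: "The metastases are evaluable 4 weeks after treatment". The next sentence is the replacement rule: "If a patient is excluded from the protocol before 4 weeks follow up, the patient will be replaced". Losses are to be accounted for as follows: "The number of patients that are being pulled out of the trial will be listed and primary reason for the exclusion will be described". The primary test is given as "Tumor response was analyzed using Fisher's exact test on objective response 6 months after treatment".

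The document defines no analysis set. It does not say how the tumours of a replaced patient are counted, and it gives no grounds for exclusion.

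**The concern.** Because treatment is a single session, a patient who is treated and then excluded before week 4 has had every randomised metastasis treated in full. The rule treats this patient like one who was never treated: a new patient comes in, and the target is filled with tumours that reached week 4. If exclusion is related to poor outcome, the response rates then describe a selected group and both can be too high. The primary objective is to evaluate as well as compare the rates, so the absolute values matter.

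The comparison can also be affected. A patient with one metastasis, or an odd number, cannot contribute equally to both arms, so losing that patient removes tumours unequally. A count of patients with reasons would not reveal this.

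The point covers losses before week 4. Losses between week 4 and the 6-month analysis also have no handling rule, but that is a separate gap.

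**Working it through.** **Inputs from the Statistical analysis section:** response 85% (bleomycin) and 70% (calcium); significance level 0.1, sidedness not stated; power 80%; 34 evaluable tumours, not stated to be per arm or in total.

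**Assumptions, not in the document:** the number of tumours lost; that every lost tumour is a failure; that the planning rates hold among evaluable tumours.

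**1. The plan's 34.** The usual two-proportion formula for 85% against 70%, one-sided 0.1 and 80% power, gives 69 per arm, so it does not reproduce 34. A total of 34 does appear if a 15-point margin is added to the 15-point difference: [0.85×0.15 + 0.70×0.30] × (1.2816 + 0.8416)² / 0.30² = 0.3375 × 4.508 / 0.09 = 16.9, that is 17 per arm. This makes 17 per arm a plausible reading but does not establish it. Both readings are used below. The present point does not depend on how 34 was derived.

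**2. Lost tumours put back as non-responders.** With n evaluable and k lost tumours in an arm, the all-treated rate is p×n/(n+k). The counts are expected values, so they need not be whole numbers.

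| Case | Calcium | Bleomycin | Difference |
|---|---|---|---|
| 17 per arm, none lost | 11.9/17 = 70.0% | 14.45/17 = 85.0% | 15.0 points |
| 17 per arm, 2 lost in each | 11.9/19 = 62.6% | 14.45/19 = 76.1% | 13.4 points |
| 17 per arm, 1 calcium lost | 11.9/18 = 66.1% | 85.0% | 18.9 points |
| 34 per arm, 2 lost in each | 23.8/36 = 66.1% | 28.9/36 = 80.3% | 14.2 points |
| 34 per arm, 2 calcium lost | 23.8/36 = 66.1% | 85.0% | 18.9 points |

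**3. The opposite starting point.** Suppose 85% and 70% are the rates among all treated tumours, and a fraction q of the failures is removed in each arm. The evaluable rate is p/(1 − (1 − p)q). With q = 0.1 the rates become 86.3% and 72.2% (14.1 points). With q = 0.2 they become 0.85/0.97 = 87.6% and 0.70/0.94 = 74.5% (13.2 points). Both rates rise, and the evaluable analysis now shows the smaller difference. Calcium has twice the failure rate (30% against 15%), so an equal fraction removes twice as many calcium failures.

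Steps 2 and 3 together show that losing failures raises both rates whenever both arms are affected. The effect on the difference can go either way, depending on how the losses fall.

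**4. What the planned listing would show.** With balanced 1:1 blocks (an assumption), two tumours lost per arm is one patient with four metastases. One calcium tumour lost is one patient with a single metastasis. Each would appear in the listing as one patient with a reason, although the first moves the difference from 15.0 to 13.4 points and the second to 18.9.

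**The case against.** The strongest reply is that the plan says excluded patients are replaced, not that their tumours are removed. Replacement could serve only to reach 34, with the earlier tumours kept. That is right as far as it goes: removal is an inference. But the target counts evaluable tumours, a tumour becomes evaluable at week 4, and no text keeps the tumours of replaced patients. Removal is the natural reading, and the plan should not leave it open.

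Second, failure of a tumour is nowhere named as a ground for exclusion, and the rule also covers patients excluded before treatment. This stands. The claim is that failures can leave the rates, not that they do.

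Third, bias between arms is limited. Neither the treating doctor nor the patient knows the syringe contents, so exclusion should not follow knowledge of the arm. Blocking within patient means that a lost patient with several tumours often removes some from each arm. An odd number by itself produces chance imbalance. All of this stands. It does not prevent inflation of both rates, or unequal loss from patients with one or an odd number of metastases.

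Two stronger readings are tempting and should not be drawn:
- A reader might take two lost calcium tumours out of 17 evaluable (11.9/19 = 63%, a 22-point gap) as the true difference. The document gives neither 17 per arm nor any number lost, and the case needs every lost tumour to be a failing calcium tumour.
- A reader might infer that adverse events of replaced patients are lost. The Secondary Objective plans registration for both treatments, and nothing removes replaced patients from it.

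Nor are losses by arm unrecoverable. Metastases are numbered and the code can be opened for a single patient. The planned listing simply does not ask for them.

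**Conclusion.** The point holds in a limited form. As written, the rule lets randomised and treated metastases leave a comparison made at tumour level, and the planned account of losses does not show how many or from which arm. The number of such losses cannot be known from the document.

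In the illustrations, one or two lost tumours in an arm lower that arm's rate by about 4 to 9 points, and the difference lies between 13.4 and 18.9 points against the planned 15. These figures assume that every lost tumour is a failure and that the planning rates apply among evaluable tumours. They show sensitivity and do not estimate a bias. The change should be made because the gap is real and cheap to close.

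**What to change.** Keep replacement as a recruitment rule only, and state the analysis separately:

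- Analyse all randomised and treated metastases under their assigned arm, counting those lost before week 4 as non-responders.
- Report the evaluable-tumour analysis with equal standing, and require both to agree before concluding non-inferiority.
- Replace the patient count with a listing by metastasis: assigned arm, last assessment and reason for loss.

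The cost is analysis wording and one listing. Assignment is already held per metastasis, and the code can be opened patient by patient without unblinding others. The date of last assessment should be in the visit records, although the document does not show the data form.

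There are two downsides. Reported response rates become slightly less favourable. Counting equal losses as non-response also pulls the arms together (15 to 13.4 points above), which by itself favours a non-inferiority conclusion. That is why neither analysis should stand alone.
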